3.3.2 Escalation phase

Once subjects reached the dose of 2.5 ml undiluted milk, they will be instructed to repeat this dose at home daily for 2 weeks. They will then come to the research unit, and will be given an increased dose of 4 ml. This will be continued for one week, with incremental increases given weekly for 16 weeks, until a dose of 200 ml is reached. If a patient is unable to increase past a particular dose they will continue on this dose until the end of the 16 week acceleration phase.

3.3.3 Maintenance phase

Patients who reach the maintenance dose of 200 ml will be instructed to continue and consume 200 ml of milk daily for 1 month. They will then undergo an oral challenge (see above), with the maximum dose of 300ml.

If this 300 ml dose is tolerated, they will be permitted to consume dairy products without restrictions and attend regular follow up visits for 12 months. It will be recommended to consume dairy at least twice weekly, if not more, to maintain the desensitization.

Subjects who tolerate less than the 200 ml upper dose will be instructed to continue their maximum tolerated dose for the 12 month follow-up period, at which time another blinded milk challenge will be performed to determine if their tolerance increased.

3.3.4 Long Term Follow-up: to assess the persistence of milk desensitization from clinical, cellular and molecular perspectives, participants will be asked to return to the research center once a year for five years following the end of the Maintenance Phase. At these visits, participants will be asked about their dairy consumption, any reactions they may have experienced in the interval between the last visit and changes in their quality of life (as assessed by questionnaire). Participants will also have the following analyses done: SPT, salivary IgA, serum milk-specific IgE, IgA and IgG4 concentrations, Glycosylation state, Vitamin D levels, and B and T cell regulatory cell phenotyping. Participants will be reminded of the importance of continuing the consumption of dairy products in the maintenance of desensitization. Participants who have completed the study will be asked to reconsent to the extension. Given that these participants may not have scheduled visits to the hospital, to lessen their inconvenience, a delegated member of the study team might make a home visit in order to obtain informed consent

3.3.4 Control Subjects: Subjects randomized to no treatment will be followed every 3-6 months as is standard in our clinic for milk allergy. They will have skin testing and blood testing as on routine follow-ups, but they will be required to fill out symptoms diaries. At the end of the study period, oral desensitization will be offered to the control patients who had not spontaneously achieved tolerance.

3.3.4 Documentation: Subjects and families will be asked to complete daily home diaries to document that daily doses were taken, as well as to report accidental ingestions, problems with dose administration, or related symptoms. Follow-up visits in addition to or in conjunction with the weekly visits for dose escalation will be at 3, 6, 9, 12 months from completion of OIT. Each visit will include a medical history and physical examination, SPT, serum milk-specific IgE, IgA and IgG4 concentrations, Vitamin D levels, and B and T cell regulatory cell phenotyping will be measured at enrollment and at follow-up visits. (see Appendix C). Biweekly or monthly Telephone follow-up of these patients will be done prior to and following reaching the maximum tolerated dose. The telephone follow-up will review symptoms

and protocols for how to treat potential reactions.

3.3.5 Adverse reactions to OIT: All patients and their caregivers (if applicable) will be provided self-administered epinephrine, along with instructions and indications for administration and education about the nature of possible reactions to the desensitization therapy. Home diary forms will be provided to record the dose, date and time taken, symptoms occurring after the dose or any other time, and medications taken each day (Appendix D).

Safety measures: The patients' caregivers will be instructed **verbally and in writing** about the recommendations to be followed after desensitization and how to **treat** possible allergic reactions. They will also be given telephone and pager numbers of investigators and nurses for direct consultation 24/7. Parents will be instructed to contact the research team should any symptoms suggestive of an allergic reaction be present (appendix E, bottom of page).:

Withdrawal from therapy: Subjects will be carefully monitored during the in hospital rush therapy phase, as well as during the home OIT phase. Instructions for treatment of reactions will be provided as above. Patients who are enrolled will be informed that in previously published studies, minor allergic reactions are common in these protocols (mild itching, abdominal discomfort) but resolve with increased time on therapy. Subjects will be withdrawn if they cannot tolerate the low dose, rush desensitization phase, if they have more than 2 or more moderate or severe reactions during the home (maintenance) OIT phase, if they experience a rare or unforeseen complication such as severe flares of eczema or chronic gastrointestinal symptoms (e.g. development of eosinophilic esophagitis) and if the parents or subjects wish to voluntarily terminate therapy.

3.3.6 : Variables measured. The following variables will be measured in each patient:

A. The primary outcome measure will be the presence of desensitization defined by the ability to tolerate 200 ml of milk 1 year after the start of the trial. This is a qualitative variable with three categories: total desensitization (200 mL of cow's milk); partial desensitization (20–200 mL); and failed desensitization (<20 mL milk). Only patients presenting total desensitization were regarded as being successfully desensitized.

B. Secondary outcome measures will be:

1. Number and severity of adverse reactions occurring after oral exposure to milk during the desensitization and follow-up phases.
2. Minimum dose of milk that triggered symptoms during the desensitization protocols or challenge tests.
3. Days until desensitization was achieved.
4. Indices of desensitization :
 - a. Change in skin prick test weal size, comparing tape transferred, cpoputor measured diameters and areas of the skin tests to milk extract.
 - b. Levels of sIgE, sIgA and sIgG4 before desensitization, during follow-up and at the end of the study.
 - c. T and B reg before desensitization, during follow-up and at the end of the study.

Sample Preparation and storage: Blood draws will be performed according to the Study Protocol Appendix C. 7-10 ml of blood will be drawn into heparinized tubes (green stopper) and 2-3 ml in red stopper tubes. Serum will be separated and frozen at -80 until processing for sIgE, IgA and IgG4 levels. Peripheral blood mononuclear cells, including T and B cells, will be isolated by Ficoll-Hypaque centrifugation. They will be resuspended at a concentration of 5×10^6 / ml, and frozen in RPMI + DMSO medium in liquid nitrogen until use for measurement of T-and Breg.

3.3.7 : Measurement of Milk specific IgE, IgA and IgG4: Milk specific IgE, IgG4, and IgA antibodies will be measured by Immunocap (Phadia, Upsalla, Sweden). This automated, matrix-based ELISA system is able to quantify specific antibodies with high accuracy, and is considered the gold standard for specific IgE measurement (62). It is ideal for pediatric samples as it requires approximately 120 μ l of blood per sample. The Immuncap system has been in use at the Montreal Children's Hospital since 2000.

3.3.8 Measurement of Regulatory T-cells: Regulatory T-cells will be measured from peripheral blood samples by flow cytometry. By definition, Treg are defined as CD4+ cells that co-express the surface marker CD25 and the intracellular marker Foxp3. 7-10 ml of blood will be procured from subjects and lymphocytes will be isolated by Ficoll-Hypaque density centrifugation. The isolated cells will be cultured at 1×10^6 / ml with milk proteins alpha, beta and kappa-casein as detailed in Noh et al (41). Following 48 hours of culture, the cells will be stained with fluorescent antibodies (CD4 APC, Foxp3 – Alexa 488, CD25 PE) and casein induced Treg populations will be determined by flow cytometry (LSRII, Becton Dickinson, Toronto, ON). Controls will include medium alone and an irrelevant antigen (gliadin). The Treg will be expressed as a percent of the total CD4+ T-cells, and the changes in Treg in response to culture with casein fractions will be followed over time. We predict that successful OIT will increase Tregs in response to milk protein exposure.

3.3.9 Measurement of Regulatory B-cells: Regulatory B-cells will be measured from peripheral blood samples by flow cytometry. By definition, Breg are defined as CD19+ cells that co-express the surface marker CD5 and the intracellular marker Foxp3. 5-10 ml of blood (as above) will be procured from subjects and lymphocytes will be isolated by Ficoll-Paque density centrifugation. The isolated cells will be cultured at 10^6 / ml with milk proteins alpha, beta and kappa-casein as detailed in Noh et al(41). Following 48 hours of culture, the cells will be stained with fluorescent antibodies (CD19 APC, Foxp3 –Alexa 488, CD5 PE) and casein induced Breg populations will be determined in an LSRII. Controls will include medium alone and an irrelevant antigen (gliadin). The Breg will be expressed as a percent of the total CD19+ B-cells, and the changes in Breg in response to culture with casein fractions will be followed over time. We predict that successful OIT will increase Bregs in response to milk protein exposure. We will also evaluate intracellular regulatory cytokines in CD19+ cells, specifically the presence of IL-10, which is expected to increase in subjects following successful OIT to milk.

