serological criteria, will be recruited for this study. 42 will undergo oral immunotherapy, while 42 will be followed as natural history controls but will be offered similar therapy, should it be successful, at the completion of one year. OIT subjects will initiate therapy with a 2-day rush desensitization treatment using oral doses of milk, in our Clinical Investigation Unit. They will then continue the highest tolerated dose of milk at home for two weeks. Subsequently, they will return for weekly increases in doses until a maximum of 200 ml of milk is ingested daily. The primary clinical outcome will be a comparison of the amount of milk consumed safely on oral challenge performed prior to OIT, when the OIT dose has reached its maximum (200 ml or highest tolerated dose) and after one year of therapy. Patients will also be followed with clinical symptom scores and adverse event diaries and we will monitor immunological parameters such as changes in milk-specific IgE, blocking antibodies (IgG4 and IgA) and regulatory T and B cells. We expect that we will be able to see important improvement in the ability to safely ingest milk and other dairy products, and this will be accompanied by significant decreases in IgE and increases in Regulatory T and B cells.

BACKGROUND INFORMATION:

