1.13 Does oral immunotherapy (OIT) give patients the ability to normally ingest dairy products? In treating allergic conditions, we may achieve either temporary **desensitization**, or complete **tolerance**. Desensitization refers to a change in the amount of food antigen needed to cause allergic symptoms; it is a temporary state and is dependent on regular exposure to the substance in question, as is done for penicillin allergic patients who require drug desensitization. When the treatment with penicillin is ended, the patient loses the ability to safely ingest it within days to weeks, unless the therapy continues. In contrast, **tolerance** refers to long-term immunologic changes associated with the ability to ingest a food without symptoms and without ongoing therapy. Both scenarios are an improvement over the status quo; desensitization as therapeutic goal allows individuals more freedom from the risk of accidental ingestion in everyday settings; however, frequent if not daily exposure to the food would be required to maintain the desensitized state. Limited reports of three subjects suggested a loss of protection within 48h to weeks after elimination of the food from the diet (45-47). A more recent trial suggested that as long as participants ingested the maintenance dose of milk at least twice a week no allergic reactions were likely to occur(48). Achieving long-term clinical tolerance would allow safe food ingestion without ongoing therapy by inducing lasting immunologic changes; given the abundance of dairy products in our diet, it is crucial, to determine if we can achieve tolerance using our clinical protocol. We will utilize oral food challenges at the end of oral immunotherapy and one month following cessation of therapy to evaluate this question.

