Through a process of stratified randomization (according to sex), participants will be randomly assigned to one of 2 study groups. The first group will receive active desensitization, and the second group will not receive any treatment but will be followed up regularly (Appendix A Table 2). Desensitization will be offered to the observation groups following the trial, should the outcome be successful in the treatment group.

3.2 Oral challenge test to milk. Prior to initiating desensitization and following treatment, the subjects will undergo a placebo controlled oral challenge to milk. These challenges will determine the level at which the children react and will be the baseline to follow their improvement in oral tolerance following therapy.

Oral challenges will be single blinded and will be performed with fresh cow's milk, with increasing doses taken orally every 10 to 15 minutes up to a total of 150ml of milk (doses of 0.1, 0.3, 1.0, 3.0, 10.0, 30.0, 45ml, 60 mL) ^{(49,82) (83)}. Patients will receive 2 challenges per day, 1 placebo and 1 with the active substance (milk). Nurses in the Medical Day Unit/Center for Investigative Medicine will prepare the food and randomize the placebo challenges. Unless contraindicated, the placebo will be soy or rice-based milk. If the challenge is negative after 150 ml of milk, results will be confirmed by means of open challenge, using 250ml of yogurt or ice cream 1 hour after completion of the blinded portion(29) according to the recommendations of the European Academy of Allergology and Clinical Immunology (5). After completing the challenge, patients will be kept under observation for at least 2 hours. Only objective symptoms will be considered to be indicative of a positive allergic reaction (29). Food challenges will be scored as positive if a single symptom or any of the following objective clinical reactions will be observed: urticaria, angioedema, wheezing, rhinitis, vomiting, diarrhea, protracted abdominal pain, exacerbation of atopic dermatitis, or shock. A single episode of vomiting will not be considered as a positive reaction, while severe and repetitive vomiting will. If the challenge is **negative**, ie, the subject is asymptomatic, he/she will be excluded from the study. Based on our experience, approximately 80% of those subjects ages 6 or greater, with positive history and positive skin tests, approached will fail the oral challenge and thus be eligible.

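### The oral challenge ends at 150 ml in one section and 300 ml in another, with no ceiling stated for later challenges, so an unchanged full responder could be recorded as losing half the tolerated volume

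*Combined protocol and SAP*

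**What the plan says.** Section 3.2 is the only general description of the challenge procedure. It sets "increasing doses taken orally every 10 to 15 minutes up to a total of 150ml of milk", lists "doses of 0.1, 0.3, 1.0, 3.0, 10.0, 30.0, 45ml, 60 mL", and states when the procedure applies: "Prior to initiating desensitization and following treatment, the subjects will undergo a placebo controlled oral challenge to milk". A negative 150 ml challenge is followed an hour later by an open challenge with 250 ml of yogurt or ice cream.

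Section 3.3.3 refers back to that procedure for children who have held 200 ml daily for one month, but changes the upper limit: "They will then undergo an oral challenge (see above), with the maximum dose of 300ml". It gives no dose steps and does not say whether 300 ml is a single dose or a running total.

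The Experimental Approach summary makes the primary clinical outcome a "comparison of the amount of milk consumed safely on oral challenge performed prior to OIT, when the OIT dose has reached its maximum" and again after one year of therapy. Section 1.13, on separating desensitization from lasting tolerance, says: "We will utilize oral food challenges at the end of oral immunotherapy and one month following cessation of therapy to evaluate this question". Appendix C places a blinded placebo-controlled challenge at Visit 24, one month after OIT stops, under the same name as the baseline challenge at Visit 2. None of these three places gives a ceiling. Appendix C lists no challenge at Visit 23, one month after escalation, although that is where section 3.3.3 would put the 300 ml one.

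Section 4.0 B names paired t-tests at p<0.05 and has no rule for a challenge completed without symptoms.

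**The concern.** A child who finishes a challenge without symptoms has shown only that the threshold lies above that challenge's ceiling. If the ceiling itself is recorded as the tolerated amount, two challenges with different ceilings give different numbers for the same child in the same state.

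The direction matters here. A lower volume at the later challenge than at the maximum-dose challenge looks like protection fading once OIT stops, which is what section 1.13 sets out to detect. If the later ceiling is the lower one, part or all of such a fall could come from the measuring range, and the best responders would contribute the largest share.

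**Working it through.** **Inputs.** Ceiling in 3.2: 150 ml total. Dose steps in 3.2: 0.1, 0.3, 1, 3, 10, 30, 45 and 60 ml. Ceiling in 3.3.3: 300 ml. Ceiling at Visit 24 and at one year: not stated. The 3.3.6 success threshold is 200 ml.

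**The plan's own figure.** 0.1 + 0.3 + 1 + 3 + 10 + 30 + 45 + 60 = 149.4 ml. This agrees with the stated 150 ml to within 0.6/150 = 0.4%, so 150 ml is a running total.

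**Are the two ceilings on one scale?** If 300 ml is a running total, the range is 300/150 = 2 times that of 3.2. If it is a single dose, it is 300/60 = 5 times the largest 3.2 step. The ranges differ either way. The figures below take 300 ml as a running total.

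**Recorded change with no true change.** Recorded amount = min(true threshold, ceiling), with the true threshold held constant.

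| True threshold (ml) | Recorded, 300 ml ceiling | Recorded, 150 ml ceiling | Change, 300 then 150 | Change, 300 then 300 |
|---|---|---|---|---|
| 100 | 100 | 100 | 0 | 0 |
| 200 | 200 | 150 | -50 | 0 |
| 250 | 250 | 150 | -100 | 0 |
| 300 or more | 300 | 150 | -150 (-50%) | 0 |

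With the exact ladder sum, the last row is 149.4 - 300 = -150.6 ml.

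**Effect on a group mean (illustration).** Suppose k of n children with both challenges are unchanged at 300 ml or more, and the rest are unchanged at or below 150 ml, so that they contribute no drop. The mean change is -150 × k/n. The documents do not say how many children would take both challenges; n = 42, the size of the OIT group, is used only for scale.

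- k = 4: -150 × 4/42 = -14.3 ml, paired t-test p = 0.044
- k = 10: -150 × 10/42 = -35.7 ml, p = 0.0009
- k = 21: -150 × 21/42 = -75 ml, p < 0.001

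These p-values follow mechanically from assuming a 150 ml re-challenge. They are not evidence that one will take place.

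**Against baseline.** Section 3.2 excludes children with a negative baseline challenge, so every enrolled child reacted within the 150 ml ladder. Baseline values are not cut off at the ceiling, and a move from baseline to either later ceiling creates no false drop.

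**The case against.** The strongest reply is that the drop depends on something the documents do not state. Section 3.3.3 overrides the 3.2 ceiling after treatment, and later challenges might keep 300 ml, in which case the artefact disappears. This stands, and the conclusion has to be conditional. The 3.2 ladder is still the default reading: it is the general procedure, it covers challenges after treatment, 300 ml appears for one challenge only, and Visit 24 carries the same label as the baseline challenge.

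A reader might also point to the 12-month blinded challenge in 3.3.3 as a place where full responders fall from 300 to 150 ml. The text does not support that. The 12-month challenge is for children who tolerate less than 200 ml, whereas the 300 ml challenge is for those who reached 200 ml. Section 3.3.3 names no further challenge for full responders.

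Three more objections have weight. Beyond its general sentence on paired t-tests, section 4.0 B spells out comparisons only for antibodies, skin tests and regulatory cells, so a paired test of maximum-dose volume against later volume is implied by the summary and not written down. Section 3.2 scores challenges as positive or negative, and nothing says that finishing 150 ml without symptoms would count as lost tolerance. The open yogurt or ice cream step means that a negative challenge does not simply end at 150 ml, although it uses a different food and is not tied to the recorded volume. These points limit how far the artefact would reach, but they do not remove the conflict between the ceilings or supply a rule for completed challenges.

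**Conclusion.** The conflict between 3.2 and 3.3.3 is real, and the ceiling at the post-cessation and one-year challenges is unspecified. The size of the effect is conditional: 150 ml (50%) for a child unchanged at 300 ml or more if the 3.2 ladder applies later, 50 to 150 ml for thresholds from 200 to 300 ml, and zero if 300 ml applies. This assumes that 300 ml is a running total and that a completed challenge is recorded at its ceiling.

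The effect is confined to comparing the maximum-dose challenge with later ones. It does not reach comparisons with baseline. Nor does it enter the three-category outcome in 3.3.6, which is not a volume difference; whether a 150 ml challenge can document 200 ml is a separate question. A reader might infer that the trial is bound to report a spurious loss of protection. The documents do not establish that, because no section states that full responders are re-challenged to 150 ml. The point should still be settled before analysis, since following the text literally puts a repeated volume on unequal scales.

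**What to change.** **Reconcile the text.** The Experimental Approach summary, sections 3.2 and 3.3.3, and Appendix C should agree on which challenges take place after treatment, the ceiling at each, and whether that ceiling is a running total or a single dose. Which ceiling to use is for the investigators to decide.

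**Change section 4.0 B.** State that a challenge completed without symptoms is right-censored at its own ceiling, and that volumes are compared between time points by a method that respects this, such as a paired interval-censored comparison. Finishing at 300 ml and later finishing at 150 ml then means above 300 followed by above 150, which is no evidence of change. As a sensitivity analysis, compare volumes cut at the lowest ceiling used in that comparison. Report the share completing each challenge.

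**Cost.** Wording and some analysis work; the analysis change needs no extra child or challenge. The common cut has a drawback: it cannot show change above the lower ceiling. With a 150 ml cut, a real fall from 300 ml to below the 200 ml success threshold could go unseen, which favours a finding of no loss. It should therefore not be the only analysis.

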Appendix C Study Design

Visit 1: Explanation, Informed Consent, Skin testing, Basic Blood testing + Immune Tolerance Evaluation (CBC, biochem, specific IgE, IgG4, IgA, Treg, Breg)

Visit 2: Physical Exam, Blinded Placebo Controlled Food Challenge

Visit 3, 4: Physical exam, 2 Day in hospital Rush initiation of Oral Immunotherapy

Visit 5: Two weeks after rush initiation, Physical exam, symptoms diary, first dose escalation

Visit 6-21: (or more if necessary) Vital Signs, Symptom Diary, Escalation of Oral Immunotherapy

Visit 22, one week after completion: Physical Exam, Symptom Diary, Basic Blood testing + Immune Tolerance Evaluation (CBC, biochem, specific IgE, IgG4, IgA, Treg, Breg)

Visit 23, One month after completion of OIT escalation: Physical Exam, Symptom Diary, Basic Blood testing + Immune Tolerance Evaluation (CBC, biochem, specific IgE, IgG4, IgA, Treg, Breg)

Visit 24: One month after cessation of OIT: Physical Exam, Symptom Diary, Basic Blood testing + Immune Tolerance Evaluation (CBC, biochem, specific IgE, IgG4, IgA, Treg, Breg) Blinded Placebo Controlled Food Challenge

Visit 25: Three months after cessation of OIT: Physical Exam, Symptom Diary, Basic Blood testing + Immune Tolerance Evaluation (CBC, biochem, specific IgE, IgG4, IgA, Treg, Breg)

Visit 26: 6 Months after completion of OIT: Physical Exam, Symptom Diary, Basic Blood testing + Immune Tolerance Evaluation (CBC, biochem, specific IgE, IgG4, IgA, Treg, Breg)

Visit 27: 9 Months after completion of OIT: Physical Exam, Symptom Diary, Basic Blood testing + Immune Tolerance Evaluation (CBC, biochem, specific IgE, IgG4, IgA, Treg, Breg)

Visit 28: 12 Months after completion of OIT: Physical Exam, Symptom Diary, Basic Blood testing + Immune Tolerance Evaluation (CBC, biochem, specific IgE, IgG4, IgA, Treg, Breg)

AVAILABLE FACILITIES AND EQUIPMENT

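### The Visit 24 challenge is meant to test tolerance off therapy, but no dosing rule stops milk, so as written it can show only maintained desensitization, at a date the text does not fix

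*Combined protocol and SAP*

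**What the plan says.** Section 1.13 separates desensitization, which depends on regular exposure, from tolerance, described as "long-term immunologic changes associated with the ability to ingest a food without symptoms and without ongoing therapy". It states that "it is crucial, to determine if we can achieve tolerance using our clinical protocol" and names the means: "oral food challenges at the end of oral immunotherapy and one month following cessation of therapy". Appendix C carries this through at Visit 24, timed one month after OIT ceases and including a blinded challenge. The only other food challenge in Appendix C is at Visit 2, before treatment.

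The dosing text is as follows.

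- **Section 3.3.3, children who pass the 300 mL challenge:** "they will be permitted to consume dairy products without restrictions and attend regular follow up visits for 12 months". The advice that follows has no end date: "It will be recommended to consume dairy at least twice weekly, if not more, to maintain the desensitization".
- **Section 3.3.3, children who tolerate less than 200 mL:** they stay on their highest tolerated dose for the 12-month follow-up and are then challenged again.
- **Appendix B:** 200 mL undiluted in weeks 17 to 52, with no milk-free step listed.
- **Section 3.3.4, Long Term Follow-up:** participants are reminded to keep taking dairy.

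The visit anchors differ. Visit 23 is labelled "Visit 23, One month after completion of OIT escalation". Visits 24 and 25 count from cessation of OIT, and Visits 26 to 28 count from completion of OIT. Section 3.3.4, Documentation, counts the 3-, 6-, 9- and 12-month visits all from completion. Neither cessation nor completion of OIT is defined.

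**The concern.** A challenge separates tolerance from desensitization only if the child has been off milk beforehand. Section 1.13 makes that distinction itself and cites limited reports, in three subjects, of "a loss of protection within 48h to weeks after elimination of the food from the diet". If milk is never stopped, a child who passes Visit 24 may be tolerant or may simply be desensitized by continued intake, and the result cannot tell which.

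At stake is the tolerance conclusion. The study title refers to inducing tolerance and section 1.13 calls the question crucial. A report that followed the plan literally could describe Visit 24 passes as tolerance when the protocol's own definition does not allow it. A second consequence is practical: with cessation undefined, sites could hold Visits 24 and 25 at quite different times.

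**Working it through.** **Step 1: reproduce the schedule.** Appendix B lists 4, 6, 8, 10, 12, 15, 20, 25, 30, 40, 50, 75, 100, 125, 150 and 200 mL from week 2 onward. That is 16 weekly increases, and 2 + 16 − 1 = 17, so 200 mL starts in week 17. This agrees with the 16 weeks of increases in section 3.3.2.

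**Step 2: date the 300 mL challenge.** Section 3.3.3 places it one month after 200 mL is reached. With 1 month = 52/12 = 4.33 weeks, 17 + 4.33 = week 21.3. Visit 23 has the same timing.

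**Step 3: date Visits 24 and 25 under each meaning of cessation.** Visit 24 = cessation + 4.33 weeks; Visit 25 = cessation + 13 weeks. The last column shows what the dosing text has a child doing just before Visit 24.

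| Meaning of cessation | Week | Visit 24 | Visit 25 | Milk intake before Visit 24 |
|---|---|---|---|---|
| Escalation ends | 17 | 21.3 | 30.0 | 200 mL daily (section 3.3.3) |
| Prescribed daily 200 mL ends at the 300 mL challenge | 21.3 | 25.7 | 34.3 | Free dairy, at least twice weekly (3.3.3); 200 mL (Appendix B) |
| Appendix B row ends | 52 | 56.3 | 65.0 | Still within the 12 months of section 3.3.3 |
| 12-month follow-up ends | 73.3 | 77.7 | 86.3 | Open-ended advice in 3.3.3; long-term reminder in 3.3.4 |

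The 12 months of section 3.3.3 run to 17 + 52 = week 69 if counted from reaching 200 mL, or to 21.3 + 52 = week 73.3 if counted from the 300 mL challenge. Either is later than week 56.3.

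No row has a milk-free month before Visit 24. Children below 200 mL are no exception: their highest dose continues for 12 months, and no stop is written for them afterwards.

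**Step 4: check visit order.** If completion means the end of escalation (week 17), Visits 26, 27 and 28 fall at weeks 43, 56 and 69. If it means the 300 mL challenge, they fall at weeks 47.3, 60.3 and 73.3. Cessation at week 52 puts Visit 25 at week 65.0, after Visit 26 on either count. Cessation at week 17 or 21.3 keeps the order, but milk continues.

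**Step 5: what a result would mean.** With milk continuing, a pass fits both tolerance and maintained desensitization. This holds whichever date is chosen, so fixing the date alone would not answer the question in section 1.13.

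**The case against.** The strongest reply is that cessation is a loose word for completion. Section 3.3.4, Documentation, counts the 3-month visit from completion, while Appendix C counts it from cessation, which suggests the two words are interchangeable. Section 3.2 speaks of challenges before and after treatment, which matches Visits 2 and 24. Visit 24 would then be the 300 mL challenge at about week 21. This reading is reasonable and supports a wording fix. It does not rescue the tolerance test: Visit 24 would coincide with Visit 23, would follow a month of daily milk, and would leave the off-therapy challenge of section 1.13 with no visit.

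It is also fair that off-therapy tolerance appears neither among the objectives in section 2.1 nor among the outcomes in section 3.3.6. That limits the weight of the point.

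Two stronger readings are tempting, and the documents support neither.

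- **Sections 3.3.3 and Appendix B contradict each other.** They need not: a child on free dairy may drink 200 mL daily to week 52 and satisfy both. Section 1.13 also cites a trial in which reactions were unlikely "as long as participants ingested the maintenance dose of milk at least twice a week", so twice-weekly intake is not shown to undo desensitization.
- **The primary outcome is damaged because the OIT arm spends a month off milk before the 1-year assessment.** That would require sites to act on the word cessation against both section 3.3.3 and Appendix B, which keep children on milk. If section 3.3.3 is followed, the 1-year comparison is not harmed by this problem.

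**Conclusion.** The point stands for the tolerance question and goes no further. Under the current dosing text Visit 24 is an on-treatment challenge. It applies to OIT children generally, including those who never reach 200 mL, and a pass cannot be reported as tolerance in the sense of section 1.13. This conclusion comes from setting the sections side by side and does not depend on the calendar.

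The dating problem is secondary. Four readings place Visit 24 between weeks 21.3 and 77.7, a range of 56.4 weeks. Taking only the end of prescribed daily dosing and the end of the Appendix B row, the gap is 56.3 − 25.7 = 30.6 weeks. These spreads depend on which readings are admitted and are not properties of the plan. They assume week counts from the first rush dose, 52/12 weeks per month, and a child on the nominal schedule; Appendix C allows extra escalation visits. The documents give no expected number of children passing 300 mL.

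The absence of the 1-year challenge from Appendix C is a separate matter and adds no weight here, though the same amendment can repair it.

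**What to change.** **Main change**

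1. Reword section 1.13 and Visits 24 and 25 so that the challenge is an on-treatment test of desensitization, and state that no tolerance conclusion will be drawn from it.
2. Count Visits 24 to 28 from one defined time point, completion of escalation. For a child who never reaches 200 mL, this can be the end of the 16-week phase in section 3.3.2. Visit 24 then falls with Visit 23, and the two can be merged. Visits 25 to 28 fall at about weeks 30, 43, 56 and 69.
3. List in Appendix C the 300 mL challenge, about one month after completion of escalation, and the challenge after one year of therapy named in the Experimental Approach. State the top dose of the latter, because the blinded series in section 3.2 totals 150 mL and section 3.3.6 asks about 200 mL.

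This costs a short text amendment. Dosing does not change, and the 300 mL and 1-year challenges are already described in the body text. The sponsor gives up a tolerance claim that the current schedule could not support.

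**Only if a tolerance result is wanted**

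Define cessation as a supervised milk-free month that starts after the 1-year primary assessment, and write it into section 3.3.3 as an exception to the advice to keep taking dairy. State which children undergo it, including those below 200 mL and those who reach 200 mL but fail 300 mL. Provide for a supervised restart. This is a design change with consent implications: some children may lose protection and need to build up again. The 9-month sample (17 + 39 = week 56) would fall inside a stop running from week 52 to week 56.3, so it should be drawn before the stop or labelled as an off-milk value.
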